### **Dissemination of Study Findings to the Community**

At study conclusion, results will be presented to Tribal colleges and their tribal community. Historically, AIs were studied for the sake of scientific research and received no benefit from participation. As such, it is important and necessary to provide the community with an understanding of the benefits they have gained from participation. In this case, a basic summary of results, including the numbers of people who successfully quit smoking, the number of smokers who participated in the study, and a basic summary of our outcome and process evaluation will be presented. In addition, all educational materials developed will be publicly available. The CAB will play a crucial role in decisions regarding dissemination to the community. All publications and presentations will require pre-approval by the Tribal colleges prior to submission or presentation.

## **VI. Plan for Monitoring and Reporting Unanticipated Problems**

### **Data and Safety Monitoring Plan.**

The purpose of this data and safety monitoring plan is to ensure the safety of study participants and the validity of data in compliance with National Institutes of Health/National Center for Minority Health and Health

Disparities/National Cancer Institute (NIH/NCMHD/NCI) requirement of Data and Safety Monitoring for Clinical Research. This section outlines essential elements of Data Safety and Monitoring (DSM) plan for this clinical research.

**Monitoring the Progress of Trials and Safety of Participants.** This study poses minimal risk to the participants as it involves the use of five Food and Drug Administration approved

products, the transdermal nicotine patch (TNP), nicotine replacement gum, nicotine replacement lozenges, varenicline, and bupropion hydrochloride. The safety of these agents has been assessed in multiple clinical trials of both smokers and non-smokers. The monitoring of the progress of the trial and the safety of participants will be overseen by [name] who is a practicing physician.

### **Plans for Assuring Compliance with Requirements Regarding the Reporting of Adverse Events (AE).**

The pharmacotherapy that will be used in this study has been approved by the Food and Drug Administration for aid in smoking cessation treatment. The adverse events associated with the TNP are few and mild and include skin irritation at the patch site and mild increases in heart rate and blood pressure. Adverse events related to nicotine gum and lozenge use are generally few and mild and can include hiccups, sore mouth and jaw, indigestion, headache, nausea, and insomnia. Studies have shown that varenicline is well tolerated, with few and mild adverse effects. The most common varenicline-related adverse effect is nausea, which is reported to be mild to moderate. Varenicline use will be monitored by the patient's primary care physician. The most common adverse effects associated with bupropion are dry mouth and insomnia. Subjects may also rarely complain of confusion, anorexia, or dizziness. Bupropion is also associated with a 1/1000 risk of seizures at the dose that will be used in this study. Factors that may increase the risk of seizures include: a history of head trauma, seizures, CNS tumors, excessive use of alcohol or cocaine, withdrawal from alcohol or benzodiazepines, and use of certain other drugs, including antipsychotics, antidepressants, theophylline, and systemic steroids. All patients will be screened for risk factors for seizures prior to recommending use of bupropion. Bupropion will only be provided to participants who have received a prescription from their primary care physician.

Participants will be prompted to discuss any adverse effects with their primary care physician or, if they do not have a primary care provider, with [name] or the on-site clinician who will work with [name]. Both subjects and physicians will be given the study office phone number (24-hour coverage) to contact study staff and/or investigators to report adverse events.

Furthermore, KUMC will be specifically asking participants weekly about potential adverse events (via our web-based communication system). Any report of an urgent/emergent or unexpected medical encounter by a study participant would automatically trigger an inquiry by our study personnel to find out what happened, create an AE report and forward that to [name] and the on-the-ground physician to review and decide whether the AE was study or study medication related and whether participant should be taken off pharmacotherapy or should be advised to stop participating in the study.

Because the anticipated level of risk involved with all possible pharmacotherapy use is low, adverse events will be recorded and reported at the completion of the study along with other study results. In addition, serious adverse events will be monitored and handled as described below:

Definition: Consistent with the definition by the FDA, a serious adverse event includes any event experienced by a study subject while on the study medication that:

- Is fatal
- Is life-threatening (subject was at risk of death from the event as it occurred)
- Is disabling or incapacitating
- Requires inpatient hospitalization or prolongs a current hospitalization
- Is a congenital anomaly in the offspring of a subject who received the study medication
- Required intervention to prevent permanent impairment or damage

Monitoring: Information about serious adverse events experienced by study subjects will be monitored by the following means:

- Report given by study subjects to study staff either in person or by telephone
- Report given to study staff by study subjects' family or friends either in person or by telephone
- Report by the subject's physician or other health care provider involved in their care
- Report from a hospital or other healthcare facility where the study subject(s) is being treated for the serious adverse event
- Other persons that may have knowledge of such serious adverse event.

Procedure: Upon receiving report of a serious adverse event:

- The study staff will page [name] (at beeper [name]) as soon as possible
- The study staff will give the necessary information to [name]
- [name] will obtain other necessary information and complete the "MED WATCH" form for each serious adverse event
- [name] will make a decision whether to stop the study medication temporarily or permanently and inform study staff of this decision
- [name] will complete the Adverse Event Report and submit completed form to the Human Subjects Committee of the University of Kansas Medical Center with 24 hours of their knowledge of the serious adverse event
- [name] will inform the manufacturer of the drug (GlaxoSmithKline or Pfizer) and fax a completed copy of the "MED WATCH" to the manufacturer and the FDA. This should be done within 24 hours of their knowledge of the serious adverse event.
- A copy of the completed "MED WATCH" form will be kept in the study file.

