participants in our tobacco cessation studies. We are comfortable with individual's self-report, mostly because we have done this successfully for years in our other tobacco cessation studies.. For Participants at a Tribal college: Participants who choose to take Chantix will also be monitored by Tribal clinic, will correspond with [name] about participants taking Chantix. All Participants will be prompted to discuss any side effects prior to starting each web-session and will be given the study office phone number (24-hour coverage) to contact study staff and/or the investigators to report adverse events. On – the - ground physician will decide if they need to directly communicate with participants when participants initiate or while they are taking medications. Our staff will also have weekly contact with participants (via our web-based communication system). [name] will provide secondary review and communicate with the on-the-ground physician or participant if need clarification on any screener responses, if the participant reports side-effects from study medications, if the participant has an Adverse Event (AE) that could be due to study or study medication related, or if the participant requests to speak with a study physician. We will follow the NIH guidelines for reporting adverse events to the Human Subjects Committee. Any problems needing medical attention will be referred to [name] (consulting physician) and the patient's personal physician. The study medication will be discontinued in patients who become pregnant, report use of any other medications that contain bupropion (e.g., Wellbutrin), or develop a contraindication. Patients will be instructed not to smoke cigarettes during treatment. Women of child bearing age who are participating in the program and requesting to use Chantix or Zyban will agree to use a form of birth control during the course of the study.

Alternatives to participating in the study are to quit cold turkey, use other smoking cessation programs, purchase nicotine gum or patches from the pharmacy, obtain a prescription for bupropion or other smoking cessation products from their physician, or continue to smoke. Other risks for participating in the study are minimal and include those associated with the inconvenience of completion of several questionnaires, email follow-up assessments, and the inconvenience of logging onto the internet for web-based counseling sessions.

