#### **IV. Inclusion/Exclusion Criteria**

##### **Eligibility**

The eligibility criteria listed below will be assessed at the recruitment visit.

Inclusion Criteria	Exclusion Criteria

 
◆ Age 18 years or older
 
◆ Currently enrolled at a Tribal college
 
◆ Have a valid telephone number and email address
 
◆ Willing to participate in all study components
 
◆ Willing to be followed-up for 6 months
 
◆ Self identifies as American Indian or Alaska Native
 
◆ Is a current smoker – self defined
 
	
 
◆ Planning to leave the college within next 6 months
 
◆ Medically ineligible as a result of screening questions
 

Medical Exclusion Criteria

For overall participation
 
 
◆ Medically ineligible as a result of screening questions
 
◆ Participant under the age of 18 years
 

For NRT (Patch, gum, lozenge):
 
 
• History of severe eczema or any serious skin problem if requested nicotine patch
 
• History of severe allergic reaction to the nicotine patch or other skin adhesives
 
• History of heart attack in the last 2 months
 
• Currently experiencing frequent angina or chest pain related to heart
 
• Currently experiencing signs and symptoms of peptic ulcer
 
• Currently receiving medications for rapid or irregular heart beat
 
• Currently experiencing signs and symptoms of severe, uncontrolled high blood pressure
 
 
For Chantix:
 
 
• Pregnant or breast feeding or planning to become pregnant in the next 6 months
 
• Currently using nicotine replacement therapy (NRT)
 
• History of suicide attempt in the past 12 months
 

- History of thoughts of suicide in the past 12 months
- History of thoughts of harming others in the past 12 months

For Zyban:

- Pregnant or breast feeding or planning to become pregnant in the next 6 months
- History of seizure disorder or head trauma
- History of severe allergic reaction to Zyban (also known as Wellbutrin, Bupropion)
- History of eating disorder, such as anorexia or bulimia, which is overeating and throwing up
- Currently taking Wellbutrin, Zyban or any other medications that contain bupropion

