How the student compares to individuals who are abstinent (normative feedback); 6) maintenance of smoking abstinence. The computer expert system will draw from a bank of several hundred messages addressing different levels of cultural, psychosocial, and environmental factors affecting smoking cessation. Intervention participants will also receive tip sheets addressing barriers specific to American Indian smokers and quitting (as identified during our formative research and Phase 1 of the study).

**Educational Curriculum:** We will adapt the ANBL materials for the tribal college population through the planned focus groups in Phase I of this study. Previous participants in formative research have stressed that cultural issues must be ingrained within the program and its accompanying education materials, not given "lip service" by putting pictures of AI people on otherwise "white" materials. We will continue to follow this guideline as we modify the materials. We will begin our educational materials modification with our current educational materials for ANBL (*see appendix*). Topics will be modified based on student input.

**Pharmacotherapy:** Pharmacotherapy is recommended for smokers trying to quit. We plan to give participants in our cessation program a choice of varenicline, bupropion, nicotine replacement therapy or no pharmacotherapy. We choose to give our participants a choice because our experience shows that we would be unlikely to recruit AI participants into a trial that requires pharmacotherapy use. Many AI are unwilling to use Western pharmacotherapy at all and others are unwilling to participate in a "drug trial", particularly if randomization is involved. All participants requesting pharmacotherapy must be medically cleared prior to receiving it.

The prescription medications (Chantix and Bupropion) and over-the-counter NRT (patch, gum, and lozenge) will be stored at KUMC in locked cabinets. KUMC will be responsible for mailing requested medications to the Polson Tribal Clinic in Polson, MT. After getting medical clearance from on-the-ground physician, participants will pick up a one month supply of study medication at the clinic. All the participants will be monitored weekly via web based system for any potential adverse events.

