**Anticipated Flow of Participants:**

Telephone Eligibility Screening Interview		
↓		
In-Person Randomization Visit (n=300)		
←      ↓      →		
Web-based weekly		
Sessions	I – ANBL (n=150)	I – FV (n=150)
1	Preparing to quit, pharmacotherapy/nrt, why do people smoke	Assessment of Risk for Heart Disease, pharmacotherapy/nrt
2	Cigarette smoking and Native people, Quit smoking date	Increasing fruit and vegetable consumption, Quit smoking date
3	Coping with Withdrawal	Physical activity
4	Traditional use of tobacco	High blood pressure
5	Stress reduction and relaxation techniques, traditional meditation techniques	Salt and sodium intake
6	Weight management, Healthy American Indian foods, exercise	High Cholesterol
7	Friends and family and quitting smoking, social support	Maintaining healthy weight
8	Staying quit – congratulations Long term maintenance	Low cost healthy eating – fruits and vegetables
Email reminders will be sent before each session so that participants will log in at the appropriate time		
12	End of pharmacotherapy treatment, feedback of program	End of program, feedback

Email reminders will be sent before each session so that participants will log in at the appropriate time		
Month 6	Assessment for current smoking status	Assessment of current smoking status

(Detailed descriptions of the weekly I-ANBL web materials are included in the appendix: will be adapted to integrate tribal college student issues identified during Phase 1 of the study)

- Telephone Screening Intake:** Research Assistants will review inclusion/exclusion criteria, smoking status and basic information about the program. We will not exclude participants who use other forms of recreational tobacco (eg – smokeless tobacco) because, based on our preliminary data, we would be excluding eligible participants if we did so. In addition, community members have encouraged us to be more inclusive for acceptability of the research in the community and make the inclusion criteria less restrictive. Therefore, we will examine use of other tobacco products in a secondary analysis. We estimate screening intake to take 10-15 minutes.

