## **Suicide/Homicide Procedures**

Serious neuropsychiatric symptoms have occurred in patients taking Chantix. These symptoms include changes in behavior, agitation, depressed mood, suicidal ideation, and attempted and completed suicide. While some patients may have experienced these types of symptoms and events as a result of nicotine withdrawal, some patients taking Chantix who experienced serious neuropsychiatric symptoms and events had not yet discontinued smoking. In most cases, neuropsychiatric symptoms developed during Chantix treatment, but in others, symptoms developed following withdrawal of Chantix therapy.

As a result, special caution must be taken if a participant reports an *increase in depressed mood, agitation, changes in behavior not typical for them, or **suicidal thoughts or action** since starting the study medication*. The suicide/homicide protocol will be instituted for all participants noting changes of this sort since starting Chantix.

The suicide/homicide protocol is as follows:

1. Ask participant to describe their symptoms in more detail.

*“Tell me more about what you are experiencing.”*

2. Assess the level of severity.

*“In general, would you say these symptoms are mild, moderate or severe?”*

3. Assess attribution of symptoms to the study medication.

*“Do you believe these symptoms are caused by the study medication or another cause?”*

4. Assess suicide/homicide risk

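### The serious adverse event definition covers only time on study medication, so serious events after stopping, or in unmedicated participants, do not clearly enter expedited reporting

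*Protocol*

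**What the plan says.** The definition is in Section VI, under the heading on compliance with adverse event reporting requirements: "a serious adverse event includes any event experienced by a study subject while on the study medication that" satisfies one of six criteria (death, threat to life, disability, hospitalisation, congenital anomaly, or intervention to prevent permanent damage).

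The procedure that follows applies on receipt of a serious adverse event report. A physician is paged and a MedWatch form completed. Reports go within 24 hours to the Human Subjects Committee, the manufacturer and the FDA. Adverse events in general are to be reported with the study results at completion.

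Other parts of the protocol bear on that time window:

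- **Suicide/Homicide Procedures (Section VI):** most neuropsychiatric symptoms arose during Chantix treatment, "but in others, symptoms developed following withdrawal of Chantix therapy".
- **Course of Action (Section VI):** a participant reporting any suicidal or homicidal ideation is advised to stop the medication at once.
- **Anticipated Flow of Participants (Section V):** the Week 12 row reads "End of pharmacotherapy treatment, feedback of program". The analysis text for the primary aim also treats Week 12 as the end of pharmacotherapy.
- **Eligibility (Section IV):** participants must be "Willing to be followed-up for 6 months".
- **Pharmacotherapy paragraph under I-ANBL (Section V):** the options are varenicline, bupropion, "nicotine replacement therapy or no pharmacotherapy".

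**The concern.** The definition decides how fast an event leaves the study team. An event classed as serious goes to outside bodies within 24 hours. One that is not follows the ordinary adverse event route, which this section reports at study end.

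The protocol describes harm that appears after Chantix is stopped, and its own safety step takes a participant with ideation off the drug. From that moment, a later attempt or admission no longer meets the wording of the definition. The same holds for any hospitalisation between Week 12 and Month 6, and for every event in someone who chose no medication. Yet the section also has physicians judge whether an event is related to the study or to the medication, so it foresees study-related events that are not drug-related.

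At stake are the completeness and speed of serious event reporting. The primary efficacy analysis is not affected.

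**Working it through.** The protocol states no figure to reproduce here. The check sets its provisions side by side and then sizes the window.

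**1. Which situations meet the definition as worded**

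| Situation | On medication? | Classed as serious? | What the protocol does provide |
|---|---|---|---|
| Admission in Week 6 while taking a study drug | Yes | Yes | Full serious event procedure |
| Suicide attempt one week after stopping Chantix | No | No | Suicide/homicide procedure, log entry, immediate physician contact |
| Admission in Month 5, drug ended at Week 12 | No | No | Inquiry, adverse event report, physician review, if the event is reported |
| Admission of a participant who chose no medication | No | No | Inquiry, adverse event report, physician review, if the event is reported |

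In the last three rows the event is recorded and reviewed. What is lost is the serious classification and a clear route to the MedWatch and 24-hour steps.

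**2. Share of follow-up outside the definition**

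Inputs: medication ends at Week 12 (flow table), and follow-up lasts 6 months (eligibility criteria). The conversion of 6 months to F = 24 to 26 weeks is an assumption.

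For a participant medicated through Week 12, the share outside is (F − 12)/F:

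- F = 24: (24 − 12)/24 = 12/24 = 50%
- F = 26: (26 − 12)/26 = 14/26 = 54%

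This counts all 12 weeks as time on drug. Anyone who starts late or stops early has a larger share outside. For a participant who takes nothing, the share is 100%.

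**3. Whole trial, by medication uptake**

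The protocol gives no uptake figure, so a range is shown. The share of all follow-up time inside the definition is at most u × 12/F, where u is the proportion taking medication.

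| Uptake u (assumed) | F = 24 | F = 26 |
|---|---|---|
| 25% | 12.5% | 11.5% |
| 50% | 25.0% | 23.1% |
| 75% | 37.5% | 34.6% |
| 100% | 50.0% | 46.2% |

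These are shares of calendar time, not of expected events. Serious drug-related events may cluster during treatment, and the protocol gives no rates from which to judge that.

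**The case against.** The strongest reply is that little is actually lost, because other provisions catch these events:

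- The inquiry trigger in Section VI applies to an urgent, emergent or unexpected medical encounter of any study participant, with no medication limit. It leads to an adverse event report and physician review.
- The suicide/homicide procedure covers changes since Chantix was started, so it reaches past the last dose. It requires a log entry and immediate physician contact whatever the level of threat.
- The Risks text in Section III promises to follow NIH guidelines for reporting adverse events to the committee, again with no medication limit.
- Some serious event steps, such as deciding whether to stop the drug and notifying its manufacturer, have no object when no drug was taken.

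All of this stands, and it rules out four stronger readings that a reader might infer.

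*That the protocol contradicts itself.* The Chantix text describes when symptoms were seen. It neither defines a serious event nor sets a reporting window. The mismatch is one of scope.

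*That these events go uncounted.* They are recorded and reviewed once they are reported.

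*That the congenital anomaly criterion is empty because "The study medication will be discontinued in patients who become pregnant".* The criterion reads "Is a congenital anomaly in the offspring of a subject who received the study medication". It looks back to past exposure, and stopping at pregnancy does not undo exposure that has already occurred. It is the one criterion that reaches beyond dosing.

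*That serious event counts would be biased between arms.* Both arms are offered the same drugs, uptake is not stated, and the protocol plans no between-arm comparison of serious events.

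The reply does not close the gap. Neither the inquiry trigger nor the suicide/homicide procedure sets a 24-hour external report. The NIH timelines are not given in the document. The suicide/homicide procedure depends on having started Chantix and does not deal with non-psychiatric events such as a seizure. The definition's verb is not strictly exhaustive, but no other definition of a serious event is given.

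**Conclusion.** The point holds as a gap in classification and expedited reporting. The definition is narrower than the risk period the protocol itself describes, than the follow-up it plans, and than the population it enrols. For a participant medicated through Week 12, 50% to 54% of follow-up is outside it, assuming 6 months means 24 to 26 weeks. For an unmedicated participant it is all of follow-up.

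The conclusion rests on reading the on-medication limit literally and on the MedWatch and 24-hour steps being tied to serious status, as the procedure states. It does not rest on any uptake figure. It also does not rest on whether the definition matches the FDA's, as the protocol says it does, because that cannot be checked from the document. The number of events that would be misclassified cannot be estimated from what the protocol gives.

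**What to change.** Reconcile the definition in Section VI with the Risks text, the pharmacotherapy options, the Suicide/Homicide Procedures and the Course of Action:

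- Remove the on-medication limit, so that serious events are classified in every randomised participant from enrolment to the Month 6 assessment.
- Keep the congenital anomaly criterion, which already refers to past exposure.
- Record at each event whether medication was being taken, which one, and the time since last use.
- State that the manufacturer is notified only where a study drug was taken, while the committee report applies to all.

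This alters what is classified and reported. It does not alter who receives a drug or when it is stopped.

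The cost is a change of wording, one or two fields on the event form and a few more reports. The wording alone does not secure capture late in follow-up. The flow table and the schedule of assessments show no contact between Week 12 and Month 6, and the weekly safety questions have no stated end date. Unless those questions are meant to continue, events in that period would come to light through spontaneous reports and the Month 6 assessment. The protocol should say which applies.
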